5.3 Strategies for Recruitment and Retention

Recruitment: Co-investigators, Drs. [name], [name] and [name], and physician colleagues seeing study participants at Michigan Bowel Control Program (MBCP) and Functional Bowel Disease (FBD) will refer potential study participants to the study team. MiChart schedule screening may also be used for identifying possible study participants.

The study team will also post the study on the UM Health Research Portal. According to NIH guidelines, we will also post the study on clinicaltrials.gov.

Retention: The study team hopes to retain study participants in the study by allowing a flexible time period between visits; as short as one week and as long as 3 weeks between visits.

5.4 Treatment Assignment Procedures

5.4.1 Randomization Procedures

Prior to the first visit, the order of TEA stimulation at the visits will be randomly assigned to each study participant. Every study participant will undergo every TEA combination (For example, ST36-100Hz, ST36-25Hz, PC6-100Hz, PC6-25Hz and Sham-TEA).

5.4.2 Reasons for Withdrawal

A study participant will be discontinued from participation in the study if:

- Any clinical adverse event (AE), laboratory abnormality, intercurrent illness, or other medical condition or situation occurs such that continued participation in the study would not be in the best interest of the study participant.
- The study participant meets any exclusion criteria (either newly developed or not previously recognized).

Study participants are free to withdraw from participation in the study at any time upon request.

5.4.3 Handling of Withdrawals

This study may be prematurely terminated if, in the opinion of the investigator or the sponsor, there is sufficient reasonable cause. Written notification, documenting the reason for study termination, will be provided to the investigator or sponsor by the terminating party.

Circumstances that may warrant termination include, but are not limited to:

- Determination of unexpected, significant, or unacceptable risk to study participants.
- Insufficient adherence to protocol requirements.
- Data that are not sufficiently complete and/or evaluable.
- Plans to modify, suspend, or discontinue the development of the TEA device.

If the study is prematurely terminated or suspended, the sponsor will promptly inform the investigators/institutions, and the regulatory authority(ies) of the termination or suspension and the reason(s) for the termination or suspension. The IRB/IEC will also be informed promptly and provided the reason(s) for the termination or suspension by the sponsor or by the investigator/institution, as specified by the applicable regulatory requirement(s).

6 Study Intervention/Investigational Device

6.1 Study Device Description

The TEA device is about 4x3cm. It is similar to a TENS (transcutaneous electrical nerve stimulation) unit that is classified by FDA as a non-significant risk device. For this study, two regular ECG electrodes will be placed on the skin surface on the preferred location as shown in Fig.1 and connected to the TEA device. This device will deliver a specified weak electrical signal. The device is powered by a small rechargeable battery and the charging will take place only when the device is not in use. The maximum current output is 10mA.

7 Study Schedule

7.1 Screening

Once a candidate is identified, a member of the study team will speak with the study participant to explain the study. The study participant may be contacted via phone and the study team member will follow the phone script and go through the pre-screen questions if interested. If the study participant is determined to be ineligible or not interested via the pre-screening contact, he or she will be excluded in the study and logged as pre-screened and ineligible or not interested.

If the study participant is eligible and interested the study team will set up the first study visit. The study participant will go through the informed consent process at the first study visit.

7.2 Visit Schedule of Events

see section 4.1 Schedule of Events for Each Visit and Appendix A for a Table Describing the Schedule of Events

7.3 Visit Compensation

Subjects in this study will receive \$200.00 per visits 1-3 and \$350.00 per visits 4 and 5.

This totals to \$1,300.00 once all study activity is completed.

The compensation is set at such a high value based on the lengthy duration of the study visits (120 minutes), the strong likelihood of discomfort due rectal dilation (the balloon inflation with the barostat procedure) and the sensitive nature of the study.

The additional payment in visits 4 and 5 is to encourage study participants to complete all five visits. It is crucial to the study design that the study participant completes all five visits.

8 Study Procedures/Evaluations

8.1 Surveys

The study participant will complete the Rome IV criteria for Irritable Bowel Syndrome at the beginning of every visit. The study participant will complete the Visual Analog Scale Pain Score twice, once during both inflations, at every visit.

9 Assessment of Safety

9.1 Methods and Timing for Assessing, Recording, and Analyzing Safety Parameters

9.1.1 Adverse Events

Adverse Event: AE is defined as any untoward medical occurrence in a study participant or clinical investigation study participant administered a pharmaceutical product regardless of its causal relationship to the study treatment. An AE can therefore be any unfavorable and unintended sign (including an abnormal laboratory finding), symptom, or disease temporally associated with the use of medicinal (investigational) product. The occurrence of an AE may come to the attention of study personnel during study visits and interviews of a study participant presenting for medical care, or upon review by a study monitor.

All AEs including local and systemic reactions will be captured on the appropriate CRF. Information to be collected includes event description, time of onset, clinician's assessment of severity, relationship to study product (assessed only by those with the training and authority to make a diagnosis, which would include MD, DDS, DMD, PA, Nurse Practitioner, or DO), and time of resolution/stabilization of the event. All AEs occurring while on study must be documented appropriately regardless of relationship. All AEs will be followed to adequate resolution.

Any medical condition that is present at the time that the study participant is screened will be considered as baseline and not reported as an AE. If a pre-existing condition or illness, which is not expected to exacerbate or worsen, deteriorates at any time during the study it should be reported as an AE.

All AEs must be graded for severity and relationship to study product.

Severity of Event: All AEs will be assessed by the clinician using a protocol defined grading system. For events not included in the protocol defined grading system, the following guidelines will be used to quantify intensity.

- **Mild:** Noticeable to the study participant, but does not interfere with study participant's expected daily activities, usually does not require additional therapy or intervention, dose reduction, or discontinuation of the study.
- **Moderate:** Interferes with the study participant's expected daily activities, may require some additional therapy or intervention but does not require discontinuation of the study.
- **Severe:** Extremely limits the study participant's daily activities and may require discontinuation of study therapy, and/or additional treatment or intervention to resolved. Severe events are usually incapacitating.

Changes in the severity of an AE will be documented to allow an assessment of the duration of the event at each level of intensity to be performed.

Relationship to Study Products: The clinician's assessment of an AE's relationship to test article (study drug) is part of the documentation process, but it is not a factor in determining what is or is not reported in the study. If there is any doubt as to whether a clinical observation is an AE, the event should be reported. All AEs must have their relationship to study product assessed using the terms: associated or not associated. To help assess, the following guidelines are used.

- **Associated** – The event is temporally related to the administration of the study product and no other etiology explains the event.
- **Not Associated** – The event is temporally independent of study product and/or the event appears to be explained by another etiology.”=

9.1.2 Expected Adverse Reactions

It is expected that study participants may discover they have an allergy to the adhesives used during on the ECG electrodes during the study.

9.1.3 Serious Adverse Events

Serious Adverse Event (SAE): An SAE is defined as an AE that meets one of the following conditions:

- Death during the period of protocol-defined surveillance
- Life-threatening event (defined as a study participant at immediate risk of death at the time of the event)
- An event requiring in study participant hospitalization or prolongation of existing hospitalization during the period of protocol defined surveillance
- Results in congenital anomaly or birth defect
- Results in a persistent or significant disability/incapacity
- Any other important medical event that may not result in death, be life threatening, or require hospitalization, may be considered a serious adverse experience when, based upon appropriate medical judgment, the event may jeopardize the study participant and may require medical or surgical intervention to prevent one of the outcomes listed above. Examples of such medical events include allergic bronchospasm requiring intensive treatment in an emergency room or at home, blood dyscrasias or convulsions that do not result in study participant hospitalization, or the development of drug dependency or drug abuse/overdose or cancer.

All SAEs will be:

- recorded on the appropriate SAE Report Form and CRF
- followed through resolution by a study clinician. The study clinician for this study is [name]. The PI is a PhD. And not an MD. As an MD, [name] will serve as the emergency contact person for the study. He is the lead of the GI physiology lab.
- reviewed and evaluated by a study clinician.

9.1.4 Unanticipated Problems

The Office for Human Research Protections (OHRP) considers unanticipated problems involving risks to study participants or others to include, in general, any incident, experience, or outcome that meets **all** of the following criteria:

- unexpected (in terms of nature, severity, or frequency) given (a) the research procedures that are described in the protocol-related documents, such as the IRB-approved research protocol and informed consent document; and (b) the characteristics of the study participant population being studied;
- related or possibly related to participation in the research (in the guidance document, possibly related means there is a reasonable possibility that the incident, experience, or outcome may have been caused by the procedures involved in the research); and
- suggests that the research places study participants or others at a greater risk of harm (including physical, psychological, economic, or social harm) than was previously known or recognized.

An incident, experience, or outcome that meets the three criteria above generally will warrant consideration of substantive changes in order to protect the safety, welfare, or rights of study participants or others. Examples of corrective actions or substantive changes that might need to be considered in response to an unanticipated problem include:

- changes to the research protocol initiated by the investigator prior to obtaining IRB approval to eliminate apparent immediate hazards to study participants
- modification of inclusion or exclusion criteria to mitigate the newly identified risks
- implementation of additional procedures for monitoring study participants
- suspension of enrollment of new study participants
- suspension of research procedures in currently enrolled study participants
- modification of informed consent documents to include a description of newly recognized risks
- provision of additional information about newly recognized risks to previously enrolled study participants.

Unanticipated problems will be recorded and reported throughout the study.

9.2 Reporting Procedures

9.2.1 Serious Adverse Events

The study will comply with IRB and FDA reporting requirements and guidelines.

9.2.2 Regulatory Reporting for Studies Not Conducted Under IND

All AEs and SAEs will be reported to the University of Michigan IRB Med.

9.2.3 Other Unanticipated Problems

Incidents or events that meet the OHRP criteria for unanticipated problems require the completion of an unanticipated problem report form. OHRP recommends that investigators include the following information when reporting an adverse event, or any other incident, experience, or outcome as an unanticipated problem to the IRB:

- appropriate identifying information for the research protocol, such as the title, investigator's name, and the IRB project number;
- a detailed description of the adverse event, incident, experience, or outcome;
- an explanation of the basis for determining that the adverse event, incident, experience, or outcome represents an unanticipated problem;
- a description of any changes to the protocol or other corrective actions that have been taken or are proposed in response to the unanticipated problem.”

9.2.4 Reporting of Pregnancy

If a study participant is pregnant she will be excluded from the study. If a study participant becomes pregnant during the study she will excluded from the remainder of the study.

9.3 Type and Duration of Follow-up of Study participants after Adverse Events

All AEs will be followed until resolved or considered stable. Follow up will be conducted by [name]. He will determine the rate of contact by accessing the severity of the AE. The reporting of AEs to IRB Med will be conducted by the study coordinator.

9.4 Safety Oversight

Data and Safety Monitoring Board (DSMB)

The first DSMB meeting will occur one month after recruitment begins. In addition to reviewing Serious Adverse Events (SAEs), the first DSMB meeting will focus on over all safety of the trial and study agent and will make a determination as to whether or not the study should proceed. The DSMB will then meet once every 6 months throughout the remainder of the study and at any time during the study in which an unexpected and possibly related SAE occurs.

The DSMB will be composed of the following members:

[name]: a Gastroenterologist and Professor of Medicine from the Division of Gastroenterology, Texas Tech University Health Science Center. [name] is an established clinical investigator in the field of functional gastrointestinal diseases. She will serve as the Chair of the committee.

[name]: a Gastroenterologist and [name]., Chair in Gastroenterology Gastrointestinal Motility Clinic from the Division of Gastroenterology at the University of Louisville. [name] is an expert in functional gastrointestinal diseases and has extensive experience in clinical trials and clinical research. He will serve as a member of the committee.

[name], PhD: an Assistant Professor of Medicine and Director of Gastrointestinal Motility, Division of Gastroenterology and Hepatology MetroHealth Medical Center, Case Western Reserve University, Cleveland, Ohio. He will serve as a member of the committee

[name]: a lead statistician from University of Michigan, Michigan Institute for Clinical & Health Research. He has over 15 years of experience on translational and health research projects across various disease area. He will serve as a member of the committee.

10 Statistical Considerations

Analysis of variance (ANOVA) will be performed to investigate the difference in each of the outcomes among 4 different sessions. Tukey's test will be used for study the differences in each of the measurements between two stimulation points (same stimulation parameters) and between two stimulation parameter sets (same stimulation points). The Pearson correlation analysis will also be performed to investigate the correlation between each of HRV parameters and the pain score or sensation threshold

. 10.1 Study Hypotheses

TEA at acupoints ST36 (a point below the knee cap) or PC6 (a point in the wrist) will be effective in reducing abdominal pain induced by rectal distention in patients with IBS-C. This hypothesis is based on published literature and our [name] experience with EA and TEA at the Johns Hopkins. [name] previous experience with EA and TEA includes: animal studies in which electrical acupuncture at ST36/PC was shown to reduce abdominal pain in a rodent model of IBS and functional dyspepsia and preliminary clinical study in patients with IBS-C showing the reduction of overall symptoms of IBS, including abdominal pain.

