Précis: This study aims to discern whether Transcutaneous Electrical Acustimulation (TEA) at acupuncture points ST36 and/or PC6 will relieve the abdominal pain associated with IBS-C. Each study participant will have 5 research visits at the Michigan Medicine GI physiology lab. During these visits, they will undergo a procedure similar to Anal Rectal Manometry performed by the GI physiology lab staff. TEA is similar to this procedure as it uses the barostat device and is performed by the GI physiology lab staff. This device has a rubber catheter that will be inserted 5-15 cm into the rectum of the study participant. Then the GI physiology staff will inflate the catheter. They will ask the study participant when they can sense the catheter. Then the GI physiology staff will continue to inflate the catheter and the study participants feel discomfort (described as the 'urge to defecate'). Then the study participant will be asked to pass the balloon (like they would pass a bowel movement).

The difference between ARM procedure and the study procedure is that there will be stimulation of acupuncture point ST36 which is below the knee cap or stimulation of acupuncture point PC6 which is just above the wrist.

At each visit there will be stimulation of only one of the points at either 100Hz or 25Hz. These are the potential combinations: ST36 100Hz, ST36-25Hz, PC6-100Hz, PC6-25Hz, Sham-TEA.

The frequency and position combination (or sham visit) is randomly assigned. The randomization determines the order in which the study participant moves through the study. Every study participant will, in the end, complete one visit at each frequency and a sham visit. The study participant will also complete surveys at the appointment. Study participants will be compensated for their participation and given a parking pass.

Objectives: Primary: Determine the best stimulation point and frequency for relieving the abdominal pain in study participants with IBS-C.

Secondary: Collect measurements of visceral hypersensitivity in study participants with IBS-C.

Population: 25 study participants, male and females, age ≥ 18 years, IBS-C satisfying Rome IV criteria

Phase: 1

Number of Sites:	1, Michigan Medicine, University of Michigan
Study Duration:	24 Months
Study participant Participation Duration:	Each visit will be 120 minutes long. There will be 5 visits total. The maximum amount of time between visits is 3 weeks. The minimum amount of time between visits is 1 week

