3.2.2 Secondary Outcome Measures

A secondary outcome of the study will be reviewing the volume and pressure measurements from the barostat device. The surveys will also be reviewed to see if the study participants have a change in their symptoms.

4 Study Design

This is a placebo-controlled trial. The placebo is the sham-TEA visit. The study will recruit 25 study participants with IBS-C. These study participants will be recruited from the UM Health Research Recruiting Registry (UM HealthResearch.org), Michigan Bowel Control Program (MBCP), Functional Bowel Disease (FBD), and the study team will screen the gastroenterology clinic schedules via MiChart.

This is a phase 1 trial. This study will only occur at the University of Michigan. There is only one group/arm of study participants. The study team plans to complete enrollment within 12 months of beginning to the study. Study participant participation will be at a minimum 5 weeks (1 week between

visits) and at a maximum 15 weeks (3 weeks between each visit). The test agent is the novel TEA device.

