10.2.1 Safety Review

Study enrollment and/or study visits will halt to at if the study team feels the study is unsafe. This would include if study participants are experiencing serious adverse events. The DSMB will meet every 3 months during the study enrollment/study visit period. If needed, the DSMB will meet more frequently to monitor the study.

This is an acute study involving 5 sessions on separate days. No treatment or intervention will be given in between sessions.

The risks involved in the study include rectal distention (a clinically approval procedure) and delivery of weak electrical current via skin surface electrodes. Any acute study session will be terminated if the patient is not tolerable to the procedure or decides to withdraw. If the safety is a concern, the remaining

study sessions will be cancelled for that particular subject. The study enrollment will be halted if serious adverse events are reported.

Safety outcome measures will include 1) pain/discomfort level during rectal distention, 2) any signs or symptoms of possible perforation or rupturing of the rectum during insertion of the rectal catheter and during rectal balloon distention, 3) any side effects due to weak electrical stimulation, such as rash or discomfort in the area of stimulation.

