10.2.2 Efficacy Review

This pilot study does not assess efficacy of the proposed TEA treatment.

The study outcomes include rectal sensation and pain during rectal distention, autonomic functions noninvasively assessed from the ECG.

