10.3 Final Analysis Plan

Analysis of variance (ANOVA) will be performed to investigate the difference in each of the outcomes among different sessions. Tukey's test will be used for study the differences in each of the measurements between two stimulation points (same stimulation parameters) and between two stimulation parameter sets (same stimulation points). The Pearson correlation analysis will also be performed to investigate the correlation between each of autonomic function parameters and the pain score or sensation threshold.

11 Source Documents and Access to Source Data/Documents

Only members of the study team will have access to source data. This includes: all information, original records of clinical findings, observations, or other activities in a clinical trial necessary for the reconstruction and evaluation of the trial.

12 Quality Control and Quality Assurance

- The study team will be present for each visit and follow the visit CRFs. The study team will go through the procedures with the GI physiology lab staff members to ensure that there is adherence to the protocol.
- The study team will sign the bottom of each study CRF at the end of the visit.

13 Ethics/Protection of Human Study participants

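### The ANOVA is planned for four sessions when every participant has five, and no named comparison tests an active modality against sham

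*Combined protocol and SAP*

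**What the plan says.** The opening of Section 10 says "Analysis of variance (ANOVA) will be performed to investigate the difference in each of the outcomes among 4 different sessions", without saying which four. Section 10.3 gives the same plan but only says the ANOVA will "investigate the difference in each of the outcomes among different sessions", with no number.

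Elsewhere the count is five. Section 10.2.1 says "This is an acute study involving 5 sessions on separate days". The Protocol Summary lists ST36 and PC6, each at 100 Hz and 25 Hz, plus sham. Section 10.2 counts four modalities and one placebo, and Appendix A shows five visits with sham as one of them.

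For pairwise work, Section 10.3 says Tukey's "test will be used for study the differences in each of the measurements between two stimulation points (same stimulation parameters"), and adds comparisons of parameter sets at the same point. Section 10 names the same two families. Neither section mentions sham.

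The aims point two ways:

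- The Protocol Summary's primary objective is selection: "Determine the best stimulation point and frequency for relieving the abdominal pain in study participants with IBS-C".
- The only hypothesis, in 10.1, is that TEA "will be effective in reducing abdominal pain induced by rectal distention in patients with IBS-C". Section 3.1 also asks which combination is best while allowing that none may be.
- Section 4 says "This is a placebo-controlled trial. The placebo is the sham-TEA visit", while Section 10.2.2 says "This pilot study does not assess efficacy of the proposed TEA treatment".

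The primary outcome (3.2.1) compares maximum tolerance before and after TEA within a visit.

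**The concern.** Sham is run in every participant, but no stated analysis is sure to use it. If the four sessions are the active ones, sham is outside the ANOVA. If all five are included, the ANOVA still names no direction and no modality, and the follow-up comparisons that are named leave sham out.

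This matters because of how the primary outcome is built. The second distension always follows the first, with 15 minutes of stimulation between them (Section 4.1). A rise in tolerance therefore mixes any TEA effect with repeat distension, elapsed time and placebo response. Only the sham session separates these.

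The ranking of the four active modalities is not biased, since a shift common to all visits cancels. But the best of four need not be better than sham. Section 10.2 says the findings will decide which treatment goes into a future trial, so the risk is carrying forward a modality when none beats sham.

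**Working it through.** **The plan's own figure.** The only derived number in Section 10 is enrolment: 20 completers at 20% dropout gives 20/(1 − 0.20) = 25, as stated. The 20 itself cannot be derived, because no alpha, power, effect size or SD is given.

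**Count of comparisons.** Five conditions give 5 × 4/2 = 10 pairs:

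| Type of pair | Pairs | Named |
|---|---|---|
| Point vs point, same frequency | 2 | 2 |
| Frequency vs frequency, same point | 2 | 2 |
| Active pairs differing in both | 2 | 0 |
| Active vs sham | 4 | 0 |
| Total | 10 | 4 |

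The documents give sham no point or frequency, so it fits neither named family.

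**Assumptions for the rest (not in the documents).** 20 completers with all sessions, two-sided 0.05, repeated-measures ANOVA on each session's pre-to-post change, and sphericity. The within-participant SD is set to 1. Effects are given as dz, the mean difference between two sessions' changes divided by the SD of that paired difference. Then δ in within-participant SDs is 1.414 × dz.

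**Four-session reading (active only).** If all four modalities have the same benefit over sham, their means are equal, the noncentrality is 0 and the rejection rate is 5%, whatever the size of that benefit. This follows from leaving sham out.

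**Five-session reading.** F has 4 and 76 df (4 × 19 = 76). Noncentrality is n × Σ(μ − mean μ)². With sham at 0 and all four active conditions at δ, this is 20 × (4/5) × δ² = 16δ² = 32 dz².

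| dz | δ | Noncentrality | Power |
|---|---|---|---|
| 0.3 | 0.424 | 2.88 | 22% |
| 0.5 | 0.707 | 8.00 | 57% |
| 0.8 | 1.131 | 20.48 | 96% |

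The noncentrality is again 8.00, and power again 57%, if all four modalities are worse than sham by dz 0.5, or if one modality exceeds the other four conditions by dz 0.5. A significant F therefore gives neither the direction nor the modality.

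**Best active against sham under no effect.** The five observed means are then exchangeable, so sham is the highest with probability 1/5. The best active mean exceeds sham with probability 4/5 = 80% (simulation: 0.7996).

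**What named sham contrasts could detect.** SE = √(2/20) within-participant SD, 76 df, 80% power per modality, noncentral t:

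| Method | Critical t | Detectable δ | Detectable dz |
|---|---|---|---|
| Unadjusted | 1.992 | 0.897 | 0.63 |
| Dunnett, 4 vs sham | 2.494 (simulated) | 1.058 | 0.75 |
| Tukey, all 10 pairs | 2.794 | 1.154 | 0.82 |

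Without sphericity, separate paired t tests on 19 df detect dz 0.66 unadjusted and 0.815 at 0.05/4 = 0.0125.

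**The case against.** The strongest defence is that this is a small Phase 1 pilot which disclaims efficacy in 10.2 and 10.2.2. Its stated primary objective is to choose a point and frequency, and the named contrasts do that. The 4 may be a leftover, since 10.3 drops it and the natural reading there is all five sessions. With five sessions, Tukey's procedure can control error over all 10 pairs, including the four with sham. The sham data will exist in any case. The 5% and 80% figures follow from the structure of the comparison and do not measure a loss on the selection objective.

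Much of this stands. The active contrasts should stay, the count conflict lies between Section 10 and the rest of the document, and Dunnett is a preference for efficiency, since Tukey on all 10 pairs would also be valid.

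It does not remove the gap. The disclaimers sit beside an effectiveness hypothesis, an objective that allows for no modality working, a placebo-controlled label and a list of methods that includes the placebo. The text names two Tukey families and sham is in neither. Reporting sham pairs would then be a decision the plan does not record, even if the error rate could be controlled.

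**Conclusion.** The concern holds and should be fixed before analysis. Section 10 conflicts with the five-session design, 10.3 does not resolve the conflict, and none of the four active-versus-sham pairs is named. As written, the effectiveness hypothesis has no specified test against the trial's placebo, and the within-visit primary criterion has no stated control.

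The session count and the list of comparisons rest on the text alone. The power and detectable-effect figures rest on the assumptions set out with them; other choices of alpha or covariance structure would move them without changing the conclusion. Even with named contrasts, 20 completers detect only fairly large effects: dz 0.75 per modality with Dunnett at 80% power. A contrast that is not significant would therefore not show that a modality equals sham, and the interval should be reported.

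**What to change.** 1. In Sections 10 and 10.3, use the same words: a repeated-measures analysis of all five conditions, four active and one sham.
2. Prespecify the four contrasts of each active modality minus sham on the pre-to-post change in maximum tolerance, Dunnett-adjusted, with confidence intervals. Keep the point and frequency contrasts with their present status, and say whether error is controlled within each family or across both.
3. In 3.2.1, judge a modality's pre-to-post rise against the same participant's sham session.
4. State that ranking best among the active modalities does not show benefit over sham, and that the top-ranked modality's sham contrast and interval will be reported with the ranking.

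The cost is a protocol amendment to 3.2.1, 10 and 10.3. No visits, participants or data are added, and enrolment stays at 25. The multiplicity penalty raises the detectable dz from 0.63 unadjusted to 0.75 with Dunnett; Tukey on all 10 pairs would need 0.82. Controlling error across both families would cost somewhat more.
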